5.1.1 General study level definitions

5.1.1.1 Analysis time points

5.1.1.1.1 Relative day

The relative study day will in general be calculated using the algorithm below:

- If the event occurred on or after the date of first study drug administration, then the following calculation is used:

$$\text{Relative Day} = \text{Date}_x - \text{Date of first dose} + 1$$

Where Date_x is the start or stop date of interest and Date of first dose is the date of first study drug administration.

- If the event occurred before the date of first study drug administration, then the following calculation is used:

$$\text{Relative Day} = \text{Date}_x - \text{Date of first dose}$$

Relative days that occur before the date of first study drug administration will be preceded by a “-”, when presented in listings.

- If the event occurred after the date of last study drug administration, then the following calculation is used:

$$\text{Relative Day} = \text{Date}_x - \text{Date of last dose}$$

Date of last dose is the date of last study drug administration. Relative days that occur after the date of last study drug administration will be preceded by a “+”, when presented in listings.

Relative day will only be computed for fully completed dates and will be missing for partial dates.

5.1.1.1.2 End date of the Treatment Period

The end date of the Initial Treatment Period will be the last scheduled visit (Week 20 Visit) date for participants who complete the Initial Treatment Period or the Early Discontinuation Visit (EDV) date for participants who withdraw from the study during the Initial Treatment Period. Similarly, the end date of the OLE Period for participants who entered the OLE Period will be the Week 124 Visit date or the EDV date. The end date of the treatment period (the Initial Treatment Period and the OLE Period) is defined as the end date of the Initial Treatment Period if the participant does not continue into OLE Period or the end date of the OLE Period if the participant enters the OLE Period.

If a participant does not have a Week 20 / Week 124 Visit or EDV, then either the date of the last visit (scheduled or unscheduled) or the date of last known dose of study drug during the Treatment Period, whichever is later, will define the end date of the corresponding Treatment Period.

5.1.1.1.3 Study periods

The following study periods are defined for the classification by study period:

- Screening: visits with dates before randomization date
- Initial Treatment Period: from randomization date to Week 20 visit date
- OLE Period: From the date of Week 20 visit to the end of study. The Week 20 Visit date will serve as the start date of the OLE Period for participants who entered the OLE Period

The Week 20 Visit date serves, according to protocol, as both the end of the Initial Treatment Period and the beginning of OLE Period. Unless otherwise stated, any assessment or measurement made prior to or on the Week 20 visit will be attributed to the Initial Treatment Period (irrespective of time of collection), and adverse events related to dosing (see Section 5.6.2) and IMP administration will be attributed to the OLE Period.

5.1.1.1.4 Mapping of assessments performed at Early Discontinuation Visit

If the EDV occurs at a scheduled visit as outlined in the schedule of assessments, then no mapping is necessary, and any early withdrawal assessments should correspond to that scheduled visit. Premature study withdrawal visit assessments that occur on a date after a scheduled visit will be assigned to the next scheduled site visit per the protocol following the last visit where assessments were available. This approach means that there is a chance that data will be mapped to a visit where a given assessment was not actually collected per the protocol schedule of assessments. Such data would subsequently not be summarized in by-visit tables (though it would be available in the listings). This possibility is understood, but it is also potentially problematic to map to the next visit where the given assessment is collected. If an assessment is infrequently performed, then the mapping could cover an unreasonably long period. It also presents the challenge that different assessments collected on the same date could be mapped to a number of different visits. Bearing these considerations in mind, the approach of mapping to the next scheduled site visit, irrespective of the schedule for the given assessment, has been adopted for the bimekizumab program.

The only exception to the above rule is for antidrug antibody (ADAb) assessments, in which all early withdrawal visit assessments will be assigned to the next scheduled visit at which ADABs are assessed. The rationale for this is that ADAB positivity is summarized over a given study period. As part of that summary, a table indicating the first visit at which ADAB positivity is observed will be prepared. In order to match the number of study participants who were ADAB positive at specific visits with the overall positivity for the period, it is necessary to ensure that ADAB positivity is attributed to a visit where such assessments were performed.

All by-visit data summaries will contain nominal visits only. Unscheduled visits will not be mapped to scheduled visits. Note that based on the early withdrawal mapping conventions described above, a mapped early withdrawal visit is considered as observed at that visit and should be summarized as such in the tables.

5.1.1.1.5 Definition of Baseline values

A Baseline value for clinical variables is defined as the latest measurement on or prior to the first dosing day of study medication, regardless of the time of the measurement, for the Initial Treatment Period and the OLE Period.

If Baseline plasma concentration is measured at a time after the first administration of study medication, then it should not be eligible to be considered as a Baseline plasma concentration. When the time of first dose is derived, it should be based on the first injection of study treatment.

5.1.1.2 Protocol deviations

Important protocol deviations are deviations from the protocol which potentially could have a meaningful impact on study conduct, or on the primary PK, key safety, or other PK/PD outcomes for an individual participant. The criteria for identifying important protocol deviations will be defined within the appropriate protocol-specific document at study start. Important protocol deviations will be reviewed as part of the ongoing data cleaning process and all important deviations will be identified and documented to confirm exclusion from analysis sets.

5.1.1.3 Treatment assignment and treatment groups

For Initial Treatment Period, treatment assignment will use randomized dose groups (Dose A and Dose B) for efficacy analysis. For safety and PK/PD analysis, treatment assignment will use dosing group as treated and stratified by low/high dosing categories based on weight, ie, weight-categorized dose groups:

- Dose A (320mg Q4W), Dose A (160mg Q4W), Dose A (all)
- Dose B (64mg Q4W), Dose B (32mg Q4W), Dose B (all)

In the OLE Period, dose group assignment will follow the same approach taken for the Initial Treatment Period. However, participants are allowed to change to PS0021 dosing based on the PK interim results or change dosing based on their weight category changes in the OLE Period. The treatment assignment group therefore will reflect dosing changes with appropriate adjustments to tables and listings when necessary.

For PK and immunogenicity analyses, participants who change dose based on their weight category changes in the OLE will be summarized according to their Baseline weight-categorized dose group.

5.1.1.4 Center pooling strategy

No pooling of centers is planned for this study.

5.1.1.5 Coding dictionaries

Medical history and AEs will be coded using the Medical Dictionary for Regulatory Activities (MedDRA®). Lab data will also be coded using Common Terminology Criteria for Adverse Events (CTCAE) grade. Medications will be coded using the World Health Organization Drug Dictionary (WHO-DD). Medical procedures will not be coded.

For MedDRA, version 23.1 or greater will be used. For WHO-DD, version Mar/2021 B3 or greater will be used. For CTCAE, version 4.03 will be used.

5.1.1.6 Multicenter studies

Disposition data will be presented by center. Other data may be presented by center when necessary.

5.1.1.7 Handling of dropouts or missing data

Details about approaches to handle missing data are described in this section. An intercurrent event is defined as discontinuation of IMP prior to Week 16.

5.1.1.7.1 Rationale for estimand

Intercurrent events have been identified within the estimands for this study because of their potential to impact efficacy assessments linked with the secondary study objectives. In order to account for the effect of any observed post-randomization intercurrent events on the efficacy analyses, the following estimand strategies will be implemented when evaluating the secondary efficacy endpoints:

- A composite estimand strategy will be used for the analysis of secondary binary endpoints (PASI90 response at Week 16, PASI75 response at Week 4, IGA 0/1 response at Week 16).
- A hypothetical estimand will be used for the analysis of the continuous secondary endpoint (CDLQI total score change from Baseline at Week 16).

The assumptions and robustness of the secondary efficacy analyses involving binary endpoints and the composite estimand strategy will be assessed through the sensitivity analyses defined in Section 5.4.1.3.

5.1.1.7.1.1 Composite estimand

A composite estimand strategy as defined in Section 5.4.1.2 allows incorporation of the intercurrent event (eg, discontinuation of IMP on or before Week 4 or Week 16) within the definition of the secondary efficacy endpoint. This intercurrent event is considered meaningful to the efficacy outcomes following administration of IMP. For example, within the proposed composite estimand framework, a randomized study participant who discontinues from IMP prior to Week 16 will be considered a treatment failure at Week 16 in the analysis of the PASI90 response at IGA 0/1 response analyses regardless of the observed PASI or IGA data.

5.1.1.7.1.2 Hypothetical estimand

The hypothetical estimand strategy is defined in Section 5.4.1.2, and involves a data-driven approach to account for the potential impact of an intercurrent event (eg, discontinuation of IMP

on or before Week 16) on the analysis of continuous secondary efficacy data. Under this framework, outcomes for study participants without an intercurrent event are analyzed as observed. Conversely, outcomes for study participants with an intercurrent event are imputed via the LOCF method a, ie, data which are missing on or after the intercurrent event will be imputed via LOCF following the method described in Section 5.1.1.7.3.

5.1.1.7.2 PK and antibody missing data

Pharmacokinetic analyses, including those of the primary PK outcome, will be based on observed data; no data will be imputed. If plasma concentration measurements are below the lower limit of quantification (LLOQ), then for calculation of the derived statistics the result will be set to half of the LLOQ.

5.1.1.7.3 Efficacy missing data

An intercurrent event is defined as discontinuation of IMP prior to the time point of interest. For secondary efficacy variables with binary responses, (eg, PASI90 at Week 16, PASI75 at Week 4, and IGA0/1 response at Week 16), study participants who have an intercurrent event will have their efficacy response variable at the timepoint of the intercurrent event and all subsequent timepoints (whether the data were observed or not) set to “nonresponse”. An observed case (OC) analysis will be performed as a sensitivity check.

For secondary continuous efficacy endpoints (CDLQI [total score] change from Baseline at Week 16), the last observation carried forward (LOCF) will be used for participants who have an intercurrent event. The observed cases (OC) method will also be performed. Definitions of intercurrent event and missing data handling specific to each secondary efficacy endpoint are provided in Section 5.4.1.2. Note, the same approach will be used for missing data not preceded by an intercurrent event, ie, LOCF for continuous endpoints and nonresponder imputation for binary endpoints. Baseline measurements are eligible to be carried forward in the event that this is the last available measurement for a participant who is missing post-Baseline data.

5.1.1.7.4 Safety missing data

For analyses of safety endpoints related to TEAEs, a complete date must be established to correctly identify the AE as occurring during treatment or not. For purposes of imputing missing components of partially reported start and stop dates for AEs, algorithms are defined in Section 5.1.1.7.5. If the intensity of an adverse event is unknown, it will be considered as severe. If the relationship to study drug is missing, it is considered as related. Note that if the seriousness of an adverse event is unknown, every attempt should be made to resolve this prior to a snapshot for an interim analysis or database lock; in the exceptional case that the seriousness of an adverse event is still missing then no imputation should be applied for this characteristic.

Vital signs, physical examination findings, growth assessments, laboratory analyses will be based on observed data; no imputation will be performed. Endpoints will be presented with descriptive statistics, as observed.

5.1.1.7.5 Missing dates and times

For PK analysis, observations with missing IMP time will be excluded and no imputation will be performed.

For analyses of AEs and concomitant medication usage, a complete date is required in order to correctly identify the AE or concomitant medication as occurring during treatment or not, and for correctly assigning an AE or concomitant medication to the ITP or OLE Period.

For purposes of imputing missing components of partially reported start and stop dates for AEs and for concomitant medication use, the algorithms listed below will be followed. Start and stop dates of AEs or concomitant medication will be displayed as reported in the participant data listings (ie, no imputed values will be displayed in data listings). Partial AE and concomitant medication start dates will be imputed as follows:

Imputation of Partial Start Dates

- If only the month and year are specified and the month and year of first dose is not the same as the month and year of the start date, then use the 1st of the month.
- If only the month and year are specified and the month and year of first dose is the same as the month and year of the start, then use the date of first dose.
- If only the year is specified, and the year of first dose is not the same as the year of the start date, then use the 1st of January of the year of the start date.
- If only the year is specified, and the year of first dose is the same as the year of the start date, then use the date of first dose.
- If the start date is completely unknown and the stop date is unknown or not prior to the date of first dose, then use the date of first dose.
- If the start date is completely unknown and the stop date is prior to the date of first dose of IMP, then set the start date to the 1st of January of the year of the end date.

Imputation of Partial Stop Dates:

- If only the month and year are specified, then use the last day of the month.
- If only the year is specified, then use December 31st of that year.
- If the stop date is completely unknown, do not impute the stop date.

If the imputed stop date is prior to the imputed start date:

- For missing start day and start month:
 - If the year of start date is the same as the year of first dose and the imputed stop date is on or after the date of first dose, then set the start date to the date of first dose.
 - Otherwise set to the 1st January of the year of the start date.
- For missing start day only
 - If the month and year of the start date is the same as the month and year of first dose and the imputed stop date is on or after the date of first dose, then set the start date to the date of first dose.
 - If the month and year of the start date is the same as the month and year of first dose and the imputed stop date is before the date of first dose, then set the start date to the 1st of that month.

In the event of ambiguity or incomplete data that makes it impossible to determine whether a concomitant medication was concomitant, or an AE was treatment emergent, the concomitant medication will be considered as concomitant, or the AE will be considered treatment emergent.

5.1.1.8 Adjustments for covariates

All analyses are descriptive and covariate adjustments are not planned.

5.1.1.9 Multiple comparisons/multiplicity

Not applicable.

5.1.1.10 Use of an efficacy subset of participants

The PK-PPS will be used to evaluate participants who have efficacy data during the treatment periods and are reasonably compliant with the conditions of the study, in addition to RS.

Two subgroup analyses are planned for efficacy endpoints: weight category and sex. Details are provided in Section 5.8.

5.2 Study Participant Dispositions

The number and percentage of participants who are screened, enrolled, and randomized will be summarized for each clinical site and overall. Number and percentages of screen failures will also be summarized in the ES, and summaries of reasons for screen failures will be produced. The participants who discontinued treatment, discontinued study, or completed the study, as well as the discontinuation reasons, will be summarized for study periods by dose group in the RS. The overall number and percentages will also be summarized.

In addition, the number and percentages of participants in each of the analysis sets (ES, RS, SS, PK-PPS, and OLS) will be summarized by treatment arm and overall.

For purposes of summarizing disposition, study participants will be considered to have completed a study period if they complete the last scheduled study visit during that study period, not including SFU visits. A participant will be considered to have completed the study as follows:

- Completion of Initial Treatment Period is defined as completing the Week 20 Visit and the completion date is the Week 20 Visit date.
- Completion of OLE Period: for participants who entered the OLE period, completion is defined as completing the Week 124 Visit, and the completion date is the Week 124 visit.
- Completion of Study: For all participants, completion of study is considered as completion of OLE Period. Participants who do not tolerate the IMP or who have an IGA response ≥ 3 (on a scale from 0 to 4) at Week 20 will be considered as withdrawn from the study due to lack of efficacy. Participants who are eligible for but elect not to enter the OLE period at Week 20 will be considered as withdrawn from the study due to consent withdrawn.

In parallel, the end date of the study for a participant will be defined considering SFU Visit: the later date of the last visit including SFU or the date of last known dose of study drug.

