4.4 End of study definition

A participant will be considered to have completed the study as follows:

- For participants who do not enter the OLE: Completion is defined as completion of the Screening Period, the Initial Treatment Period, and the SFU Visit.
- For participants who enter the OLE: Completion is defined as completion of all periods of the study (ie, Screening Period, Initial Treatment Period, OLE Period, and the SFU Visit).

The end of the study is defined as the date of the last participant's last visit.

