6. Participant has an IGA response ≥ 3 (on a scale from 0 to 4) at Week 20.

Investigators should contact the Medical Monitor to discuss whether a participant is to be withdrawn from the study if any of the following events occur:

7. Participant develops an illness that would interfere with his/her continued participation.
8. Participant or caregiver is noncompliant with the study procedures or medications in the opinion of the Investigator.
9. Participant takes prohibited concomitant medications as defined in this protocol (Section 6.5.2).
10. Participant does not tolerate the IMP.
11. Study participants **must be referred** immediately to a mental healthcare practitioner (ie, licensed psychiatrist or clinical psychologist) and may be withdrawn from the study based upon the Investigator's judgment of benefit/risk for either of the following:
 - Active suicidal ideation as indicated by a positive response (“Yes”) to Question 4 of the “Since Last Visit” version of the C-SSRS.
 - Moderately severe major depression as indicated by a PHQ-9 score of 15 to 19 if this represents an increase of 3 points compared to last visit.

The mental health consultation will be documented in source documentation.

12. Any study participant who develops a clinically important infection or recurrent infections not responsive to standard therapy during the study must:
 - Discontinue IMP until resolution of the infection.
 - The Investigator should use clinical judgement in deciding whether the study participant should restart IMP and contact the Medical Monitor and UCB study physician to confirm the participant's suitability for continued participation in the study.

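### SAP 5.2 books Week 20 intolerance as lack of efficacy and defines study completion differently from Protocol 4.4, so disposition reasons and completion counts will be wrong as written

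*SAP*

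**What the plan says.** SAP 5.2 sets three rules that matter here.

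- **Reason at Week 20.** "Participants who do not tolerate the IMP or who have an IGA response" of 3 or more "at Week 20 will be considered as withdrawn from the study due to lack of efficacy".
- **Study completion.** "For all participants, completion of study is considered as completion of OLE Period". For disposition, a period counts as completed for participants "if they complete the last scheduled study visit during that study period, not including SFU visits".
- **Declining the OLE.** "Participants who are eligible for but elect not to enter the OLE period at Week 20 will be considered as withdrawn from the study", with consent withdrawn as the reason.

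The protocol reads differently.

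- **Section 4.4.** For a participant who does not enter the OLE, "Completion is defined as completion of the Screening Period, the Initial Treatment Period, and the SFU Visit". For one who does, every period must be completed, again including the SFU Visit.
- **Section 7.2.** Withdrawal of consent is item 2. IGA of 3 or more at Week 20 is item 6, a mandatory withdrawal. "Participant does not tolerate the IMP" is item 10, where withdrawal is to be discussed with the Medical Monitor.
- **Section 4.1.** Intolerant and IGA 3-or-more participants are both described as withdrawn, but no common reason is assigned.
- **Table 1-1, footnote b.** Not wishing to continue into the OLE is a foreseen path.

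**The concern.** Not tolerating the drug is a safety reason for leaving; an IGA of 3 or more is an efficacy reason. A participant with clear skin who cannot tolerate the IMP would be tabulated as an efficacy failure. This is a small two-dose study whose objectives include safety, so readers will look at the reasons for leaving, by dose group, as separate questions.

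Completion is affected separately. A participant who does all that Protocol 4.4 asks without entering the OLE is reported as having withdrawn consent. An OLE participant who skips the SFU Visit is reported as having completed. The study completion rate will therefore not match the protocol's definition, and SAP 6.2 does not tell the reader so.

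**Working it through.** There is no plan figure to reproduce, so the check is a comparison of texts followed by simple proportions.

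**Classification by type of participant**

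| Participant | SAP 5.2 | Protocol 4.4, read literally | Protocol 4.1 and 7.2 |
|---|---|---|---|
| Intolerant at Week 20, no OLE, SFU done | Withdrawn, lack of efficacy | Completed | 4.1: withdrawn; 7.2 item 10: withdrawal to be discussed |
| IGA 3 or more at Week 20, SFU done | Withdrawn, lack of efficacy | Completed | Withdrawn |
| Eligible, declines OLE, SFU done | Withdrawn, consent withdrawn | Completed | Declining is not listed as a withdrawal event |
| In OLE to Week 124, SFU missed | Completed | Not completed | Not addressed |

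The reason given in the first row comes from the SAP alone. Rows three and four are direct conflicts between SAP and protocol, and they run in opposite directions. In rows one and two the protocol also conflicts with itself.

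**Where the departure is recorded.** SAP 6.4.2, Change #11, says the completion definition was updated to align with protocol amendment 2. The amendment 2 summary (Protocol 10.11.2) lists no change to Section 4.4. The current protocol, amendment 3, on which the SAP says it is based, keeps the two-path definition. SAP 6.2, the list of changes to protocol-planned analyses, does not mention it.

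**Scale.** SAP Section 3 plans at least 40 participants, 1:1, so 20 per arm. One recoded participant moves a percentage by 1/20 = 5.0 points within an arm, or 1/40 = 2.5 points overall.

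**Illustration.** The counts below are assumptions and are not in the documents. Everyone attends Week 20 and the SFU Visit, and all others finish the OLE.

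| Intolerant / IGA 3 or more / decline OLE | Completed, SAP 5.2 | Completed, Protocol 4.4 literal | Completed, 4.4 with first two groups withdrawn | Lack of efficacy, SAP (actual) | Intolerance, SAP (actual) |
|---|---|---|---|---|---|
| 1 / 2 / 1 | 36/40 = 90.0% | 40/40 = 100% | 37/40 = 92.5% | 3 (2) | 0 (1) |
| 2 / 4 / 2 | 32/40 = 80.0% | 40/40 = 100% | 34/40 = 85.0% | 6 (4) | 0 (2) |

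Whatever the true number, intolerance shows as zero in the study-withdrawal reasons.

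**The case against.** The case for leaving this alone is that it touches little. SAP 5.6.2.2 tabulates TEAEs leading to study withdrawal and TEAEs leading to IMP discontinuation by weight-categorized dose group, with exposure-adjusted rates, and both are named secondary safety endpoints. SAP 5.2 also summarizes reasons for stopping treatment, reports Initial Treatment Period completion at Week 20 regardless of OLE entry, and defines a participant's study end date with the SFU Visit in view. SAP 5.6 expects only a few participants not to enter the OLE. The completion change was not silent, since the amendment history records it.

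Most of this stands, and it rules out several stronger readings that a reader might infer.

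- **That the report conceals tolerability failures.** It does not: intolerance reported as an adverse event remains visible in the TEAE tables. Only the study-withdrawal reason in the disposition table is affected.
- **That efficacy is made to look worse.** Only a label changes. The secondary efficacy endpoints are at Weeks 4 and 16, and Week 20 disposition enters none of them.
- **That the distortion falls mainly on the higher dose.** No document gives adolescent tolerability by dose.
- **That every non-OLE participant is a protocol completer wrongly called withdrawn.** This is clean only for eligible decliners. For the other two groups, Protocol 4.1 also says withdrawn.

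The objection does not remove the error. The separate TEAE table means that one participant can be an adverse-event withdrawal in one output and an efficacy withdrawal in another. The amendment-history entry gives a rationale that the amendment summary does not support.

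**Conclusion.** The point holds as a disposition-reporting error. Followed as written, SAP 5.2 gives a wrong reason for every participant who leaves at Week 20 for intolerance. It also gives a completion count that differs from Protocol 4.4 for eligible OLE decliners and for OLE participants without an SFU Visit. The size is 5 percentage points per recoded participant in an arm of 20; the total depends on counts that the documents cannot give. The primary PK analysis, the efficacy estimates and the TEAE tables do not change. It should be corrected, but it does not threaten the study's conclusions.

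This rests on two readings: that the SAP sentence concerns the Week 20 decision on continuing, as in Protocol 4.1, and that Protocol 4.4 governs what counts as completion. For intolerant and IGA 3-or-more participants the second reading is open, because the protocol's own sections disagree.

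**What to change.** 1. Split the rule in SAP 5.2: IGA of 3 or more at Week 20 is lack of efficacy; not tolerating the IMP is adverse event or intolerance, taken from the recorded primary reason.
2. Report eligible participants who decline the OLE as not entering by choice rather than as consent withdrawn, and count them as completers if they finish the Initial Treatment Period and the SFU Visit.
3. Apply the Protocol 4.4 completion definition, SFU Visit included, or list and justify the departure in SAP 6.2. Correct the stated rationale in either case.
4. Reconcile Protocol 4.1 and 7.2 with 4.4 for intolerant and IGA 3-or-more participants before programming. Applying steps 1 and 3 without this would make the same person both completed and withdrawn.

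The cost is SAP wording and one disposition derivation, plus a protocol clarification for step 4. No new data should be needed, provided the eCRF holds a primary reason for Week 20 cases. The protocol sentence requiring that reason sits in Section 7.3 on loss to follow-up, so its use here should be confirmed.
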